4.4.3. Blinding

The unblinded pharmacist at the site will refer to the electronic treatment key provided for the trial by the SDCC to determine the treatment assignments for the subjects. The pharmacist will maintain a hard copy of the treatment key (provided by the SDCC) under locked/secured conditions and will follow the randomization code.

As described in Section 4.4.1 above, the placebo and auranofin capsules are similar in appearance, but not perfectly identical. They will be stored in identical containers. Study staff administering them and study subjects will not be informed of their minor differences in appearance nor of the treatment assignments of subjects. The treatment assignment codes used by staff administering the medication will not reveal the treatment assignments of subjects. In addition, the laboratory personnel performing evaluations will be blinded to treatment assignment.

The protocol contains no explicit provisions for emergency unblinding. According to DMID policy, the study medical monitor responds to requests for emergency unblinding, and instructs the SDCC to release treatment codes only if necessary, to ensure that the subject receives appropriate clinical care.

4.5. Efficacy and Safety Variables

4.5.1. Efficacy Variables

[Table 4](#) and [Table 5](#) summarize the efficacy variables and time points for the asymptomatic and symptomatic populations, respectively.

Table 4: Efficacy Variables for the Asymptomatic Study Population

Outcome Type	Outcome	Time points, Asymptomatic amebiasis group	Time points, Asymptomatic giardiasis group
Primary	Parasitological response (no detection of cysts or trophozoites on microscopic exam or negative antigen detection)	Day 7	Day 5
Secondary	Parasitological response (no detection of cysts or trophozoites on microscopic exam or negative antigen detection)	Days 3 and 5	Day 3
	Rate of decrease in trophozoite/cyst load by qPCR in stools	Days 3, 5, and 7	Days 3 and 5
	Negative stool antigen test	Days 3, 5, 7, and 14	N/A
	Sustained cure (no detection of cysts or trophozoites by microscopic exam or negative antigen detection)	Days 14 and 28	Days 14 and 28
	Relapse (same strain) or re-infection (new strain) with positive stools by genotyping the initial vs. subsequent strain.	Day 14 and/or 28	Day 14 and/or 28

Table 5: Efficacy Variables and Time Points for the Symptomatic Study Population

Changes from outcomes for the asymptomatic population are shown in blue:

Outcome Type	Outcome	Time points, Symptomatic amebiasis group	Time points, Symptomatic giardiasis group
Primary	Resolution of diarrhea ^a	Day 7	Day 5
Secondary	Parasitological response (no detection of trophozoites on microscopic exam ^b)	Days 3, 5, and 7 ^c	Day 3 and 5 ^c
	Rate of decrease in trophozoite/cyst load by qPCR in stools	Days 3, 5, and 7	Days 3 and 5
	Negative stool antigen test	Days 3, 5, 7, and 14	Days 3 and 5
	Sustained cure (no detection of trophozoites by microscopic exam) ^d	Days 14 and 28	Days 14 and 28
	Relapse (same strain) or re-infection (new strain) with positive stools by genotyping the initial vs. subsequent strain.	Day 14 and/or 28	Day 14 and/or 28
	Time to resolution of diarrhea	Assessment over the study period	Assessment over the study period

^a New outcome for the symptomatic population^b The definition of parasitological response was revised to allow for cysts and remove the antigen test.^c Moved from primary to secondary outcome.^d The definition of “cure” was updated to match the updated definition of “parasitological response”.

Diarrhea will be assessed by self-report at each study visit. All other primary and secondary outcomes for both disease groups are measured on stool samples. Subjects will provide stool samples on Days 1, 3, 5, 7(window +1 day), 14 (window +3 days) and 28 (window +3 days). The specimen will be stored in a cooler with ice pack for transport to the laboratory. All laboratory personnel will be blinded, and the specimens de-identified.

- Testing of stool samples will be performed by the icddr,b Parasitology Laboratory or Rajshahi Hospital laboratory and will include:
 - Wet mount for ova and parasite examination;
 - TechLab EIA to detect *E. histolytica* and *Giardia* to identify protozoal infections;
 - PVA fixation for concentration and trichrome staining for ova and parasite examination
 - Qualitative PCR to detect *E. histolytica* and *Giardia*
- Off-site testing of stool samples at UCSD will include quantitative *E. histolytica* or *Giardia* testing performed at UCSD on shipped aliquots of DNA extracted from positive stools at icddr, b. De-identified DNA specimens labeled with the subject code will be obtained from stools on Days 1, 3, 5, 7, 14, and 28 following enrollment. Quantitative PCR assays have been developed based on the small subunit rRNA gene, which is highly conserved among *E. histolytica* (Taniuchi, 2011) and *Giardia* isolates (Haque, 2007).

Safety variables include solicited adverse events, vital signs, and clinical labs. These are the same for the two disease groups and study populations. The only exception is that although diarrhea is recorded for both populations, it is considered an efficacy rather than safety variable for the symptomatic population, because it is an eligibility criterion and an efficacy endpoint. In other words, since everyone enrolls with diarrhea, their

subsequent diarrhea is probably not due to the treatment. Solicited events and vital signs are recorded during planned visits until the Day 28 visit. Vital signs are recorded during every planned follow-up visit.

Solicited events are AEs that are known to occur with this study product. Adverse event data is collected at each visit using specific questions and/or targeted physical examination. Based on the adverse reactions listed on the package insert, these include: loose stools or diarrhea, abdominal pain, nausea with or without vomiting, constipation, anorexia, flatulence, dyspepsia, dysgeusia, pruritus, hair loss, urticarial, stomatitis, conjunctivitis, glossitis, hematuria, and rashes. As noted above, diarrhea is considered an adverse event only in the asymptomatic population as it is a condition for enrollment in the symptomatic population. Physical examinations look for abdominal pain, hair loss, urticaria, rashes, stomatitis, conjunctivitis, and glossitis. In the symptomatic population, solicited AEs are not collected that are related to any prescribed metronidazole. Adverse event collection continues until Day 28 (following three half-lives of the drug). Each solicited adverse event described above is graded as Mild (Grade 1) if it “Does not interfere with daily activity”, as Moderate (Grade 2) if it “Interferes with daily activity”, and as Severe (Grade 3) if it “Prevents daily activity (incapacitating)”. Grading for vital signs, also collected on every visit, is given in [Table 6](#). Furthermore, hematology, biochemistry, and urine labs are analyzed on Study Day 7. Grading for these adverse events is given in [Table 7](#). Some laboratory grading ranges were modified in protocol updates; these modifications are displayed in the table. Laboratory results are graded according to the protocol effective on the date the sample was collected. The effective date is the date that the site received IRB approval for the version and began implementing that version. (The effective date is later than the protocol version date, which indicates when the version was approved by DMID.) The first subjects in the study enrolled under Protocol Version 4.0, so laboratory ranges for earlier protocol versions are not displayed. The effective dates are as follows: Version 4.0: 18Oct2016, Version 5.0: 12Dec2017, Version 6.0: 07Aug2018, Version 7.0: 23Jul2019.

Table 6: Vital Signs Grading Scale

Vital Signs*			
Vital Signs	Mild (Grade 1)	Moderate (Grade 2)	Severe (Grade 3)
Fever (°C) **	37.8-38.4	38.5-38.9	>= 39.0
Hypertension (systolic) mm Hg	141-150	151-155	>155 or an ER visit or hospitalization for malignant hypertension
Hypertension (diastolic) mm Hg	91-95	96-100	>100 or an ER visit or hospitalization for malignant hypertension
Hypotension (systolic) mm Hg	85-89	80-84	<80 or an ER visit or hospitalization for hypotensive shock
Bradycardia – beats per minute ***	50-54 or >10 bpm less than baseline if baseline < 60	45-49 or >15 bpm less than baseline if baseline < 60	<45 or > 20 BPM or less than baseline if baseline < 60, or an ER visit or hospitalization for arrhythmia
Tachycardia – beats per minute	101-115	116-130	>130 or an ER visit or hospitalization for arrhythmia

* Subjects should be at rest for at least 15 minutes prior to vital sign measurements
 ** Oral temperature; no recent hot or cold beverages or smoking
 *** When resting heart rate is between 60-100 beats per minute. Pulse and Blood Pressure assessed at Visit 1 (Day 1) will be considered baseline. Sinus bradycardia among some healthy subject populations, for example, conditioned athletes maybe acceptable

Table 7: Laboratory Adverse Event Grading Scale

NOTE: For grading ranges that were updated in protocol revisions, all ranges are shown in the below table, with their corresponding protocol versions. No subjects were enrolled under Protocol Versions 1-3, so ranges from those versions are omitted. Events are graded according to the protocol version that was active at the time of the event. Effective dates are: Version 4.0: 18Oct2016, Version 5.0: 12Dec2017, Version 6.0: 07Aug2018, Version 7.0: 23Jul2019

Hematology	Mild (Grade 1)	Moderate (Grade 2)	Severe (Grade 3)
WBC 10 ⁹ /L (Decrease)	Version 4: 3.0-3.9 Versions 5-7: 3.0 – 3.4	2.0-2.9	<2.0
WBC 10 ⁹ /L (Increase)	Version 4: 11.1-13.0 Versions 5-7: 13.1-13.9	Version 4: 13.1-15.0 Versions 5-7: 14.0-15.0	>15.0
Hgb g/dL (Decrease) (Female)	Versions 4-6: 9-11.4 Version 7: 9.1-10.9	7.5-9.0	<7.5
Hgb g/dL (Decrease) (Male)	Versions 4-6: 9-12.4 Version 7: 9.1-10.9	7.5-9.0	<7.5
Hgb g/dL (Increase)	Versions 4-6: N/A Version 7: 18.1-18.5	Versions 4-6: N/A Version 7: 18.6-19.0	Versions 4-6: N/A Version 7: >19.0
Platelets 10 ⁹ /L (Decrease)	Version 4: 100-149 Versions 5-7: 100-130	50-99	<50
Platelets 10 ⁹ /L (Increase)	Version 4: 451-480 Versions 5-7: 551-600	Version 4: 480-500 Versions 5-7: 601-700	Version 4: >500 Versions 5-7: >700

Chemistry	Mild (Grade 1)	Moderate (Grade 2)	Severe (Grade 3)
BUN mg/dL	Version 4: 25-60 Versions 5-7: 31-60	Versions 4-7: 60-70 [†] Version 8: >60 and ≤70	>70
Creatinine umol/L ¹ (Increase) (Male)	Version 4: 107-176 Versions 5-7: 134-176	177-221	>221
Creatinine umol/L ¹ (Increase) (Female)	Version 4: 98-161 Versions 5-7: 134-176	Version 4: 162-202 Versions 5-7: 177-221	Version 4: >202 Version 5-7: >221
AST IU/L males (Increase)	Version 4: 38.1-200 Version 5: 60.1-200 Versions 6 and 7: 70.1-200	201-300	>300
AST IU/L females (Increase)	Version 4: 32.1-200 Version 5: 60.1-200 Versions 6 and 7: 70.1-200	201-300	>300
ALT IU/L males (Increase)	Version 4: 41.1-200 Version 5: 60.1-200 Versions 6 and 7: 70.1-200	201-300	>300
ALT IU/L females (Increase)	Version 4: 31.1-200 Version 5: 60.1-200 Versions 6 and 7: 70.1-200	201-300	>300

Urinalysis	Mild (Grade 1)	Moderate (Grade 2)	Severe (Grade 3)
Protein	1+	2+	3+ or hospitalization or dialysis

¹Conversion factor from mg/dL: <http://onlinelibrary.wiley.com/doi/10.1002/9780813818825.app3/pdf>

²Trace protein at screening (Visit 00B) is acceptable for inclusion into the study.

[†]Values of 60 fall into both Mild and Moderate categories for protocol versions 4-7 and will be classified as Mild.

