However, the protocol endpoints and study population were revised because after screening 2,396 people during 17 months with only 34 enrolling into the study, it became apparent that enrolling 136 asymptomatic subjects would be infeasible. For this reason, eligibility criteria were revised, starting with protocol version 5, to enroll symptomatic rather than asymptomatic adult patients (still with amebiasis or giardiasis). The goal, as before, was to enroll 68 in each disease group and randomize in a 1:1 ratio within each disease group to receive either auranofin or placebo. The dosing regimen was unchanged, but the primary outcome was revised for the new (symptomatic) study population. The new primary outcome is resolution of diarrhea (less than 3 loose stools / 24 hours) by Day 7 for the symptomatic amebiasis group and by Day 5 for the symptomatic giardiasis group. Furthermore, in version 7 of the protocol, a new site was also added (Rajshahi Medical College Hospital), after which randomization was stratified by site as well as disease group. The protocol revision specified that the asymptomatic and symptomatic subjects would be analyzed separately.

The study populations, study design, and primary outcome for each of these populations are summarized by protocol version in [Table 1](#):

Table 1: Summary of Study Population, Study Design, and Primary Outcome by Protocol Version

Protocol Versions	Study Population	Target Sample Size	Treatment Allocation	Dosing Regimen	Primary Outcome
1-4	Asymptomatic amebiasis	68	1:1 (auranofin: placebo)	7 days	Parasitological response (no detection of cysts or trophozoites on microscopic exam or negative antigen detection) by Day 7
	Asymptomatic giardiasis	68	1:1 (auranofin: placebo)	5 days	Parasitological response (no detection of cysts or trophozoites on microscopic exam or negative antigen detection) by Day 5
5-7	Symptomatic amebiasis	68	1:1 (auranofin: placebo) ^a	7 days	Resolution of diarrhea (less than 3 loose stools / 24 hours) by Day 7
	Symptomatic giardiasis	68	1:1 (auranofin: placebo) ^a	5 days	Resolution of diarrhea (less than 3 loose stools / 24 hours) by Day 5

^a Randomization was also stratified by site for subjects enrolled under protocol version 7 because a second site was added in that protocol version.

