6. Vital signs (oral temperature, pulse, and blood pressure) are all within normal protocol-defined ranges
7. Laboratory tests (blood urea nitrogen, creatinine, AST, ALT, white blood cells, platelets, hemoglobin) are all within protocol-defined ranges.

Subjects will be eligible for enrollment with the following laboratory values:

- Blood urea nitrogen less than or equal to 30 mg/dL
- Creatinine less than or equal to 133umol/L
- AST or ALT less than or equal to 70.0 U/L
- White cell count between 3.5 and 13.0 inclusive($10^9/L$)
- Platelets between 131 and 550 ($10^9/L$) inclusive
- Hemoglobin between 11.0 and 18.0 gm/dL inclusive

8. Urinalysis with no greater than trace protein. If a high protein is confirmed to be due to menstruation, it should be repeated.
9. Women of reproductive potential⁴ must have a negative urine pregnancy test within 72 hours of starting study medications.

⁴Female subjects who are surgically sterile via tubal sterilization, bilateral oophorectomy or hysterectomy, who have been postmenopausal for greater than 1 year are not considered to be of reproductive potential.

10. Female subjects participating in sexual activity that could lead to pregnancy must be using and continue to use highly effective⁵ contraception for a total of 4 months after enrollment.

⁵Highly effective methods of contraception are defined as having low failure rates (i.e. less than 1% per year) when used consistently and correctly and may include, but are not limited to, abstinence from intercourse, monogamous relationship with a vasectomized partner, male condoms with spermicide, diaphragm with spermicide, intrauterine devices, and licensed hormonal methods. Females on effective forms of birth control will continue while on the study and for the follow-up period of 4 months total. The method and compliance of birth control used will be confirmed and documented at all study visits.

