14.3.5 Displays of Laboratory Results

Figure 22: Laboratory Results: Distribution on Baseline and Day 7 by Laboratory Parameter, Treatment Group, and Gender (where appropriate) - Asymptomatic Amebiasis Group (N=68)

[figure not shown]
Figure will be repeated for the symptomatic amebiasis group.

Grading criteria were changed during the course of the study. The most conservative grading thresholds will be displayed. Other ranges will be shown as dashed lines or indicated in a footnote.

Figure 23: Laboratory Results: Distribution on Baseline and Day 7 by Laboratory Parameter, Treatment Group, and Gender (where appropriate) - Asymptomatic Giardiasis Group (N=68)

Figure will be repeated for the symptomatic giardiasis group.

Grading criteria were changed during the course of the study. The most conservative grading thresholds will be displayed. Other ranges will be shown as dashed lines or indicated in a footnote.

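### Symptomatic laboratory grades follow the protocol version in force on the sample date, so the pooled severity tables mix hemoglobin and AST/ALT scales and the mild-abnormality counts have no single definition

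*SAP*

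**What the plan says.** SAP 4.5.1 sets the grading rule: "Laboratory results are graded according to the protocol effective on the date the sample was collected". The note above SAP Table 7 repeats it: "Events are graded according to the protocol version that was active at the time of the event". The Introduction explains that "eligibility criteria were revised, starting with protocol version 5, to enroll symptomatic rather than asymptomatic adult patients", so the symptomatic population is covered by version 5 onward. The effective dates are "Version 5.0: 12Dec2017, Version 6.0: 07Aug2018, Version 7.0: 23Jul2019".

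Table 7 prints the ranges by version. For low-hemoglobin Grade 1, the male row reads "Versions 4-6: 9-12.4 Version 7: 9.1-10.9" and the female row "Versions 4-6: 9-11.4 Version 7: 9.1-10.9". The high-hemoglobin row is not applicable through version 6 and carries three grades in version 7. The AST and ALT Grade 1 floor is 60.1 IU/L in version 5 and 70.1 in versions 6 and 7.

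SAP 9.6 presents severity by study day and arm, separately for each disease group and study population. The shells for Tables 46-50 are marked for repetition in the symptomatic population, with no version column. The changed criteria are addressed for Figures 22 and 23 only, where "The most conservative grading thresholds will be displayed" and other ranges appear as dashed lines or in a footnote.

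**The concern.** One numeric result can be Grade 1 in one period and ungraded in another, and both periods go into the same cell of a severity table. A pooled mild-abnormality rate then depends partly on when subjects were enrolled. Anemia and raised liver enzymes are among the reactions that the protocol lists for auranofin (Protocol 2.3.1 and 9.1), so readers will look to these tables for absolute rates in symptomatic patients. They could not tell how much of a Grade 1 count comes from the patients and how much from the scale.

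**Working it through.** The plan states no abnormality rate, so there is no figure to reproduce. The check grades the same value under each version and then illustrates the shift.

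**Time in force.** From the SAP 4.5.1 dates, version 5 ran from 12Dec2017 to 07Aug2018, 238 days. Version 6 ran from then to 23Jul2019, 350 days. The older hemoglobin scale therefore applied for 238 + 350 = 588 days after the switch to symptomatic subjects. This is time in force, not a count of subjects.

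**Same value, different grade (Table 7 cut-points).**

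| Result | Version 5 | Version 6 | Version 7 |
|---|---|---|---|
| Hgb 12.0, man | Grade 1 | Grade 1 | none |
| Hgb 11.4, woman | Grade 1 | Grade 1 | none |
| Hgb 9.0 | Grade 1 and Grade 2 overlap | same overlap | Grade 2 |
| Hgb 18.2 / 18.8 / 19.5 | none | none | Grade 1 / 2 / 3 |
| AST or ALT 65 | Grade 1 | none | none |
| AST or ALT 250 | Grade 2 | Grade 2 | Grade 2 |

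The affected intervals are hemoglobin 11.0-12.4 in men and 11.0-11.4 in women, hemoglobin above 18.0, exactly 9.0, and AST/ALT 60.1-70.0. WBC, platelet, creatinine and BUN Grade 1 ranges are the same in versions 5 to 7.

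**Link to eligibility.** The symptomatic criteria require "Hemoglobin between 11.0 and 18.0 gm/dL inclusive". On the version 7 scale no eligible subject can be graded for low or high hemoglobin at screening. On the older scale a man at 11.0-12.4 is Grade 1 at baseline. (The SAP excerpts this criterion from version 7. Version 4 lists the same limits; the criteria of versions 5 and 6 are not given.)

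**Where it enters the tables.** Hemoglobin has its own severity shell, Table 48. AST and ALT have none among Tables 46-58 and enter only through Table 46, any laboratory parameter. Table 48 also has no low/high columns, so version 7 high-hemoglobin grades would be added to low-hemoglobin grades.

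**Illustrative size.** The distributions are assumptions, not in the documents, and no eligibility floor is applied. For hemoglobin, P(Grade 1 or worse, low) = Φ((c − mean)/SD), with c = 12.45 (men) or 11.45 (women) for versions 5-6 and c = 10.95 for version 7, allowing for rounding to 0.1. For men with mean 14.0 and SD 1.3:

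- Versions 5-6: Φ((12.45 − 14.0)/1.3) = Φ(−1.19) = 11.7%.
- Version 7: Φ((10.95 − 14.0)/1.3) = Φ(−2.35) = 0.9%.

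| Assumed distribution | Older scale | Newer scale |
|---|---|---|
| Men, Hgb mean 13.5 / 14.0 / 14.5, SD 1.3 | 21.0% / 11.7% / 5.7% | 2.5% / 0.9% / 0.3% |
| Women, Hgb mean 12.0 / 12.5 / 13.0, SD 1.0 | 29.1% / 14.7% / 6.1% | 14.7% / 6.1% / 2.0% |
| AST log-normal, median 22 / 28 / 35, log-SD 0.5 | 2.2% / 6.4% / 14.0% | 1.0% / 3.3% / 8.3% |

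For hemoglobin, older means versions 5-6 and newer means version 7. For AST, older means version 5 and newer means versions 6-7.

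**Pooled rate.** With a share w of samples before version 7, the rate is w × 11.7% + (1 − w) × 0.9% for men with mean 14.0. This gives 3.6%, 6.3% and 9.0% for w = 25%, 50% and 75%. The documents do not give w.

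**The case against.** The rule is explicit and stated in advance, and every range and effective date is printed. It keeps the tables aligned with the laboratory adverse event criteria that sites were applying. Figures 22-23 display the changed thresholds. For low hemoglobin and AST/ALT only the Grade 1 boundary moves, apart from the overlap at 9.0; low-hemoglobin Grade 3 and AST/ALT Grades 2-3 are constant. Hemoglobin means, medians, ranges and changes from baseline (Tables 60 and 64) and the raw values in Listings 25-28 do not depend on grading. Screening falls on Days -4 to -1 and the next test on Day 7 (+1), so nearly every subject has both values on one scale, and a man who enters with a low value shows as Grade 1 in the baseline row.

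All of this stands, and it rules out several stronger readings:

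- **The treatment comparison is biased.** Randomization is concurrent and 1:1 within strata, so the arms are graded alike within a version. Only chance imbalance remains.
- **High hemoglobin goes unseen before version 7.** It is ungraded, but it still appears in the raw listings and in the minimum and maximum.
- **Grading is confounded with site.** The second site did join in version 7, but no planned laboratory table compares sites or periods.
- **A table will show the AST/ALT rate falling at version 6.** No shell reports an AST- or ALT-specific severity rate.

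None of this gives Tables 46 and 48 a single definition of Grade 1. The remedy in the figures does not reach the tables.

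**Conclusion.** The point holds as a modest defect in descriptive safety reporting. Following the stated rule, the symptomatic repeats of Table 48 (hemoglobin) and Table 46 (hemoglobin, AST and ALT), for both disease groups, combine different scales. Their absolute mild-abnormality counts depend on the unstated share of subjects sampled before each change.

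The grade changes follow directly from Table 7 and need no assumption. The percentages rest wholly on assumed distributions, and symptomatic enrollment by version is not given, so the real mixing could be trivial or large. A reader might conclude that the laboratory safety data cannot be interpreted. The documents do not support that: the arm contrast, the unchanged higher grades, the hemoglobin summary statistics and the raw listings all remain usable.

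**What to change.** In SAP 4.5.1, Table 7 and 9.6, derive the grades for the symptomatic versions of Tables 46-50, in both disease groups, from the recorded numeric values on one fixed, pre-specified scale whatever the sample date. The Table 7 version 7 ranges are the natural choice, and they also remove the overlap at hemoglobin 9.0. Add a footnote giving the number of values whose grade differs from the one under the version in force.

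Keep version-in-force grading for Tables 44-45, the relatedness Tables 51-58 and the listings. Relatedness cannot be derived afterwards for values that had no grade when they were collected, so Tables 51-58 should not be regraded.

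The cost is SAP wording, one derived variable and the footnote; no new data are needed. There are two downsides. Summary counts may differ from site-reported laboratory adverse events. The version 7 scale also counts fewer mild low-hemoglobin values than versions 5-6 did, including men at 11.0-12.4, who are below the site's normal range of 12.5-17.5 (Protocol Appendix C). The footnote should disclose both.
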